3.3 Study Procedures and Flowchart

Study subjects or subjects' parent/legal representative will be informed by study staff of the possibility for enrollment in the PMS study while attending a visit at the participating clinic or hospital, for the purpose of vaccination with MenACWY-CRM according to the local routine clinical care.

Informed consent must be obtained from the subject, or where applicable, the subject's parent(s) or legally acceptable representative(s) prior to the performance of any study related procedures.

At the visit, for each subject, data will be collected on the respective source document and then recorded on the appropriate section of the CRF.

Visit 1 - Day 1

- Written informed consent from the subject or subject's parents/legal representative, will be obtained.
- It will be checked whether subject conforms to inclusion and exclusion criteria (see section 4.0).
- Medical history will be collected and recorded on the Medical History CRF.
- A physical exam/assessment, including height, weight and body temperature (preferably axillary) will be performed and results recorded before vaccination.
- Demographic data will be collected and recorded.
- The study vaccine will be administered intramuscularly in the deltoid, preferably of the non-dominant arm. If the investigator determines that the subject's health on the day of vaccination temporarily precludes vaccination, according to the indication reported in the vaccine leaflet, the visit may be rescheduled.
- The subject will be observed closely for at least 30 minutes in the clinic after vaccination, with appropriate medical treatment readily available in case of a rare anaphylactic reaction following the administration of vaccines. Any local or systemic reaction observed within 30 minutes post vaccination will be recorded in the Adverse Event CRF.
- All subjects, or, where applicable, the subject's parents/legal representative, will be dispensed a Diary Card with instructions on how to complete it:
 - Days 1-7: record all local (erythema, induration, pain) and systemic (chills, nausea, malaise, myalgia, arthralgia, headache, rash, fever) reactions, all other AEs and SAEs, and all medications used to treat them;
 - Days 8-29: record all medically attended AEs and SAEs and all medications used to treat them.

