- The subjects, or, where applicable, the subject's parent/legal representative, will be instructed to contact the investigator immediately should the subject manifest any signs or symptoms they perceive as serious.
- The subject or subject's parent/legal representative will be informed of the date of the study termination by a phone call at Day 29, if deemed necessary by the investigator.

☎/✉ - Day 29

- If Diary Cards are returned during a routine visit at the study center, the investigator will review local and systemic reactions, AEs and SAEs with the subject or subject's parent/legal representative. Any new and/or clarified findings, additional

to what was already reported in the Diary Card, will be documented in the subject's medical record;

- If Diary Cards are returned using the PASE, the site staff should carefully review and assess the entries on the Diary Card; for all AEs and SAEs throughout the 28 days following vaccination the site staff should follow up by phone with the subject or subject's parent/legal representative; any new and/or clarified findings should be documented in the subject's medical record.
- All local and systemic reactions noted by the subject or subject's parent/legal representative will be reviewed and recorded on subject's medical record and on the appropriate Local and Systemic Reaction CRF.
- All AEs and SAEs will be collected, reviewed and recorded on the Adverse Events CRF.
- All concomitant medications used to treat AEs and SAEs during the trial will be collected and recorded.

All SAEs will be monitored until resolution and/or the cause is identified. If a SAE remains unresolved at study termination, a clinical assessment will be made by the investigator and the NVD regional physician to determine whether continued follow up of the SAE is required.

Should the Diary Card not be retrieved within 10 days after Day 29, subject or subject's parent/legal representative will be contacted by phone to assess the occurrence of adverse events, determine the subject's clinical status and complete study termination. All information will be recorded by the site staff on the subject's medical record and collected in the appropriate section of the CRF.

At least three phone contact attempts (at three subsequent days) will be made by the study staff to reach the subject or subject's parent/legal representative.

[figure not shown]
- Study termination will be completed for all subjects and noted on the CRF.

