6.2.1 Immediate Hypersensitivity Reactions

The occurrence of immediate hypersensitivity reactions up to 30 minutes after vaccination will be recorded on the Adverse Events CRF.

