6.2.2 Local and Systemic Reactions¹

The occurrence of selected indicators of reactogenicity (listed below), which by definition, can only occur up to 7 days post vaccination, will be recorded on the “Local and Systemic Reactions” appropriate CRF. These will be summarized in the final report under the category “solicited adverse events” to differentiate them from other adverse events which were not solicited.

- **Local Reactions**: erythema, induration and pain.
- **Systemic Reactions**: chills, nausea, malaise, myalgia, arthralgia, headache, rash, fever.

Subjects or subjects’ parent/legal representative will be asked to measure body temperature and record all solicited local and systemic reactions and unsolicited AEs for 7 days following vaccination on a Diary Card. The study site will then collect the Diary Card after Day 29 by mail using PASE provided, or at a subsequent clinic or hospital visit. If the Diary Card will not be returned, telephone contacts will be made to solicit assess the occurrence of solicited reactions and adverse event and determine the subjects clinical status.

All other medically attended AEs and associated concomitant medications will be recorded throughout the 29 day follow-up period.

¹ Local and systemic reactogenicity is referred to as “solicited adverse events” to differentiate those events that were solicited on a checklist from other adverse events collected during the trial.

Site staff should consult the MenACWY-CRM Korean prescribing information for additional information concerning contraindications, hypersensitivity, adverse reactions, special warnings and precautions for use.

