* Mild(1), Moderate(2), Severe(3) : Chills, Nausea, Malaise, Myalgia, Arthralgia, Headache

*None(1), Urticarial(2), Other(3) : Rash

* $\geq 38^{\circ}\text{C}$ (1) : Fever

Table 4.1.6 Summary of Systemic AE by Max severity

Safety Set		1*	2*	3*	Total
		n (%)	n (%)	n (%)	n (%)
Age (2-23 months)	Change in eating habits				
	Sleepiness				
	Irritability				
	Vomiting				
	Diarrhea				
	Rash				
	Fever				
Age (2-5)	Change in eating habits				
	Sleepiness				
	Irritability				
	Vomiting				
	Diarrhea				
	Rash				
	Fever				
Age (6-10)	Chills				
	Nausea				

Safety Set		1*	2*	3*	Total
		n (%)	n (%)	n (%)	n (%)
	Malaise Myalgia Arthralgia Headache Rash Fever				
Age (11-18)	Chills Nausea Malaise Myalgia Arthralgia Headache Rash Fever				
Age (19-34)	Chills Nausea Malaise Myalgia Arthralgia Headache Rash Fever				
Age (35-55)	Chills Nausea Malaise Myalgia Arthralgia Headache Rash Fever				
Age (≥56)	Chills Nausea Malaise Myalgia				

Safety Set		1*	2*	3*	Total
		n (%)	n (%)	n (%)	n (%)
	Arthralgia				
	Headache				
	Rash				
	Fever				

* Mild(1), Moderate(2), Severe(3) : Chills, Nausea, Malaise, Myalgia, Arthralgia, Headache, Change in eating habits, Sleepiness, irritability, vomiting, diarrhea,

*None(1), Urticarial(2), Other(3) : Rash

* $\geq 38^{\circ}\text{C}$ (1) : Fever

Table 4.1.7 Summary of Solicited AE by day (<6 years)

Safety Set		30 min	6hr	2 days	3 days	4 days	5 days	6 days	7 days	Total
		n (%)	n (%)	n (%)	n (%)	n (%)	n (%)	n (%)	n (%)	n (%)
Solicited AE	Local AE									
	Injection site tenderness									
	Injection site erythema									
	Injection site induration									
	Systemic AE									
	Change in eating habits									
	Sleepiness									
	Irritability									
	Vomiting									
	Diarrhea									
	Rash									
	Fever									
Total										

Table 4.1.8 Summary of Solicited AE by day (≥ 6 years)

Safety Set		30 min n (%)	6hr n (%)	2 days n (%)	3 days n (%)	4 days n (%)	5 days n (%)	6 days n (%)	7 days n (%)	Total n (%)
Solicited AE	Local AE									
	Injection site pain Injection site erythema Injection site induration									
	Systemic AE									
	Chills Nausea Malaise Myalgia Arthralgia Headache Rash Fever									
Total										

Table 4.1.9 Summary of Solicited AE by day

Safety Set		30 min n (%)	6hr n (%)	2 days n (%)	3 days n (%)	4 days n (%)	5 days n (%)	6 days n (%)	7 days n (%)	Total n(%)
Age (2-23 months)	Injection site tenderness									
	Injection site erythema									
	Injection site induration									

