6.2.3 Analysis of Unsolicited AE

All unsolicited AEs and MAAE recorded in the CRF will be mapped to preferred terms using the most recent MedDRA dictionary and classified by System organ class (SOC) and Preferred Terms (PT). Under the classification standard of MedDRA terms, and all AEs excluding the AEs whose causal relation with the study medication is ‘Not Related’ shall be treated as AEs whose causal relation cannot be excluded {hereafter “Adverse Drug Reaction(ADR)”}.

- ① The frequency and percentage of unsolicited AE (Day 1-7) and MAAE (Day 1-29) according to the expected, serious, severity, frequency, action taken, outcome, relationship to MenACWY-CRM regarding occurred AE will be calculated.
- ② The frequency of unsolicited AEs (Day 1-7) and MAAE (Day 1-29) will be classified into the preferred terms according to the expected, serious, severity, frequency, action taken, outcome, relationship to MenACWY-CRM.
- ③ The number of subjects and percentage of SAE/Serious ADR (SADR), unexpected AE/ADR,

	CONFIDENTIAL :	Last Update Date
	THIS DOCUMENT AND INFORMATION CONTAINED HEREIN IS PROPRIETARY TO COMPANY AND IS NOT TO BE DISCLOSED WITHOUT THE WRITTEN PERMISSION OF COMPANY.	20-APR-2018
STATISTICAL ANALYSIS PLAN(V6.0)		

MAAE/ADR, unsolicited AE/ADR and continuous solicited AE/ADR will be calculated according to the preferred terms. And the number of subjects and percentage by study vaccination number of SAE/Serious ADR (SADR), unexpected AE/ADR, MAAE/ADR, unsolicited AE/ADR and continuous solicited AE/ADR will be calculated according to the preferred terms in infants 2 to 23 months.

- ④ For subjects excluded from safety per protocol set[†], the number of subjects and the percentage of SAE/Serious ADR (SADR), unexpected AE/ADR, MAAE/ADR, unsolicited AE/ADR and continuous solicited AE/ADR will be calculated according to the preferred terms. And the number of subjects and percentage by study vaccination number of SAE/Serious ADR (SADR), unexpected AE/ADR, MAAE/ADR, unsolicited AE/ADR and continuous solicited AE/ADR will be calculated according to the preferred terms in infants 2 to 23 months.

[†] Subject excluded from safety per protocol set: Except for subjects who didn't receive study vaccination and follow-up failure.

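### Protocol 3.3 puts reactions seen in the first 30 minutes on the Adverse Event form, Protocol 6.2.2 and the SAP tables treat checklist symptoms as solicited, and no rule reconciles them

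*Protocol*

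**What the plan says.** Four places in the protocol govern where an early reaction is written down.

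- Section 3.3, Visit 1: "Any local or systemic reaction observed within 30 minutes post vaccination will be recorded in the Adverse Event CRF". This is not limited to allergic reactions or to events off the checklist.
- Section 6.2.1 is narrower: "The occurrence of immediate hypersensitivity reactions up to 30 minutes after vaccination will be recorded on the Adverse Events CRF".
- Section 6.2.2 covers the checklist symptoms, which "can only occur up to 7 days post vaccination, will be recorded on the “Local and Systemic Reactions” appropriate CRF". The first 30 minutes are not excepted.
- Section 3.3, Diary Card: "Days 1-7: record all local (erythema, induration, pain) and systemic (chills, nausea, malaise, myalgia, arthralgia, headache, rash, fever) reactions". At Day 29, the reactions that the subject or parent noted are "reviewed and recorded on subject's medical record and on the appropriate Local and Systemic Reaction CRF".

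In the SAP, the solicited-by-day tables open with a 30-minute column. It appears in V1.0 (Tables 4.1.3 and 4.2.3) and is still there in V4.0, the latest version whose shells are supplied, for example "Table 4.1.7 Summary of Solicited AE by day (<6 years"). V6.0 section 6.2.2 still promises summaries at each time point by reference to Appendix 1. On the unsolicited side, V6.0 section 6.2.3 says "All unsolicited AEs and MAAE recorded in the CRF will be mapped to preferred terms", and does not say what happens to a checklist symptom found on the Adverse Event form.

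**The concern.** Solicited reactions and unsolicited events (both Day 1 to 7) are separate components of the primary safety objective and are reported as separate percentages. Injection-site pain or nausea ten minutes after vaccination is a checklist symptom within Day 1 to 7, so the SAP expects it among the solicited reactions. Protocol 3.3 tells the site to enter it on the other form.

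If the analysis follows the form, the event lands in the unsolicited tables, with a causality rating that also feeds the adverse drug reaction tables. If the parent or subject also enters it in the diary, it sits on both forms. If it is not in the diary, no written step carries it to the solicited form, and the 30-minute column may be incomplete.

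**Working it through.** The plan states no figure on this point, so the check is a comparison of instructions followed by an illustration.

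**Routing of a checklist symptom seen by staff within 30 minutes**

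| Source | Destination |
|---|---|
| Protocol 3.3, Visit 1 | Adverse Event form |
| Protocol 6.2.1 | Adverse Event form only if hypersensitivity |
| Protocol 6.2.2 | Local and Systemic Reactions form |
| Protocol 3.3, Day 29 | Local and Systemic Reactions form, if noted by subject or parent |
| SAP shells V1.0 to V4.0 | Solicited tables, 30-minute column |

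Notes b and d to Protocol Table 3.3-1 keep the sources apart: study personnel collect the 30-minute data, and the diary supplies the daily solicited reactions.

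**Is this only a mismatch between versions?** No. SAP V1.0 (last updated 6 March 2013) predates Amendment 1 (approved June 2013). It therefore belongs with the protocol text supplied, and it already has the 30-minute column.

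**Effect on the endpoints, counted per subject (SAP V6.0 section 4.1)**

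| Recorded on | Analysis follows | Solicited % | Unsolicited % | Event count | Any-AE % |
|---|---|---|---|---|---|
| AE form only | form | may be too low | may be too high | unchanged | unchanged |
| Both forms | form | unchanged | may be too high | too high | unchanged |
| AE form only | symptom | correct | correct | correct | unchanged |
| Both forms | symptom, duplicates kept | correct | correct | too high | unchanged |

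In the first row, the solicited percentage falls only if the subject has no other solicited entry in that row of the table. The unsolicited percentage rises only if the subject has no other unsolicited event.

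**What the Adverse Event form can supply.** Protocol 3.3.1 lists date of onset but no time, and no diameter. Protocol 6.2.3 grades severity by interference with daily activity, whereas SAP 6.2.2 grades erythema and induration in millimetres. A record moved to the solicited side may thus have neither a 30-minute time stamp nor a size grade.

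**Illustration only.** The documents give no rate for symptoms in the first 30 minutes. Let p be the share of subjects with such a symptom, assumed to be 0.5% to 5%.

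- Protocol version 1, 3,000 evaluable: 3,000 × 0.005 = 15; 3,000 × 0.05 = 150 subjects.
- SAP V6.0, 3,000 + 600 = 3,600 evaluable: 3,600 × 0.005 = 18; 3,600 × 0.05 = 180 subjects.

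Let u be the true unsolicited share. If every such symptom were classed by form, independently of other events, the reported share would be 1 − (1 − u)(1 − p).

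- u = 5%: 1 − 0.95 × 0.995 = 5.48%; 1 − 0.95 × 0.95 = 9.75%.
- u = 10%: 1 − 0.90 × 0.995 = 10.45%; 1 − 0.90 × 0.95 = 14.5%.

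These are upper cases for the chosen p and u. If events are classified by symptom, the shift is zero.

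**The case against.** A reader might infer that immediate symptoms are in fact misclassified or double counted, so that solicited rates are biased down and unsolicited rates up. The documents do not support that, for four reasons.

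- Footnote 2 to Protocol 6.2.3 ties the unsolicited label to not being on the checklist, not to the form used. Applied by symptom, pain at ten minutes stays solicited.
- SAP V6.0 section 6.2.3 lists continuous solicited events separately from unsolicited ones, so a solicited symptom coded in MedDRA is not automatically unsolicited.
- The CRF and Diary Card are not supplied. The reactions form may already have a 30-minute field.
- Only protocol version 1 is supplied in full. The amendment descriptions list no change to the Visit 1 sentence, but Amendment 1 revised sections 3 and 6 without reproducing the text. Whether the sentence survives cannot be confirmed. The V5.0 and V6.0 shells are also absent.

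These arguments turn a claimed bias into a risk, but they do not remove the conflict. The footnote is a note on naming. No SAP version turns it into a derivation rule, so two programmers could reasonably produce different tables. The listing of continuous solicited events does not say how a non-continuing checklist symptom on the Adverse Event form is handled.

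**Conclusion.** The point holds as a conflict in recording instructions, confirmed between protocol version 1 and SAP V1.0, with no reconciling rule in any later SAP version supplied. A checklist symptom seen by staff in the first 30 minutes may be classed as unsolicited, recorded on both forms, or missed from the solicited endpoint and its 30-minute column.

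The size cannot be derived from the documents. The illustrative shifts rest on assumed values of p and u, on independence, and on classification wholly by form. Double recording leaves the share of subjects with any AE unchanged, so the exposure is confined to the split between solicited and unsolicited, the event counts, and the completeness of the 30-minute column. It is worth correcting because those two percentages are reported separately and the correction is small.

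**What to change.** 1. **Protocol 3.3, 6.2.1 and 6.2.2.** Reconcile the three sections. Checklist symptoms observed within 30 minutes go on the Local and Systemic Reactions form at a 30-minute time point, with diameter where applicable. Only hypersensitivity reactions and non-checklist events go on the Adverse Event form. Serious and medically attended events are still also recorded there. First check whether the Visit 1 sentence stands in the protocol version in force.

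2. **SAP 6.2.2 and 6.2.3.** Add a rule: a non-continuing Adverse Event form term with onset on Day 1 to 7 that matches a solicited symptom for that age group is counted once per subject as solicited and left out of the unsolicited tables, but stays in the SAE and MAAE tables. Where onset time or size was not collected, the 30-minute column or millimetre grade is reported as missing.

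The cost is a clarification for sites on form completion, a 30-minute field if the reactions form lacks one, and one programming rule. Rule 2 corrects classification and double counting in data already collected. It cannot recover times or sizes that were never recorded, so it does not replace step 1. SAP V6.0 took effect on 23 April 2018 and the trial period ends about 22 May 2018, so step 1 has about a month in which to act and rule 2 must do most of the work.

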Table 3.3-1: Times and Events Table

Visit Type	Clinic Visit	 / 
Study Day	Day 1	Day 29
Study Visit Window	n/a	-4/+7
ICF	X	
Exclusion/Inclusion	X	
Medical history	X	
Physical exam/assessment ^a	X	
Study vaccine administered	X	
Immediate hypersensitivity reactions ^b	X	
Diary Card Dispensed	X	
Diary Card Collected and/or Reviewed ^c		X
Assess/review Local/Systemic Reactions ^d		X
Assess/review AEs and SAEs ^e		X
Concomitant medications ^f	X	X
Study Termination ^g		X

- a. Physical examination must be performed by a qualified health professional designated within the Site Responsibility Delegation Log.
- b. Data on immediate reactions will be collected by the study personnel for all subjects for 30 minutes post-injection.
- c. Diary card review at Day 29 will be performed over the phone or during a routine visit at the study center. Please refer to protocol Section 3.3.
- d. Subject's parents/legal representative will record local and systemic solicited reactions on the Diary Card daily for 7 days after each study vaccination.
- e. Assess AEs and SAEs according to Safety Assessment Table in the Protocol (Table 3.1-1). All SAEs will be monitored until resolution and/or cause identified. If an SAE remains unresolved at study termination, a clinical assessment will be made by the investigator and the NVD regional physician to determine whether continued follow up of the SAE is needed.
- f. Collect concomitant medications according to Safety Assessment Table in the Protocol (Table 3.1-1)
- g. Any subject who terminates the study during the Post-Vaccination period is recommended to undergo Day 29 study-related procedures.

Figure 3.3-1: Study Procedure Flowchart - detailed

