4.3 Withdrawal of Subjects from Therapy or Assessment

The subject, or where applicable, the subject's parent/legal representative can withdraw consent for participation in the study at any time without penalty or loss of benefit to which the subject is otherwise entitled. The investigator can withdraw a subject if, in his or her clinical judgment, it is in the best interest of the subject or if the subject cannot comply with the protocol.

If a subject withdraws from the study, the reason for withdrawal should be documented in the subject's medical record and reported in the CRF. If the withdrawal of a subject resulted from an AE, the information should be recorded in the CRF.

Withdrawn subjects will not be replaced.

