6.2.5 Methods and Timing for Assessing and Recording Safety Parameters

All study subjects will be observed for at least 30 minutes after a vaccination for evidence of immediate reactions in general and in particular for symptoms of allergic phenomena

(such as rashes, itching, or other allergic manifestations). Each subject, or where applicable, the subjects' parent/legal representative will be instructed to complete a Diary Card for 28 days following vaccine administration, describing: local reactions, systemic reactions, and all AEs for 7 days after vaccination; medically attended AEs, SAEs and associated concomitant medications throughout 28 days following vaccination. If a local and systemic reaction continues beyond 7 days after vaccination, the subject or subject's parent/legal representative should note this on the Diary Card and note the start and stop dates of the event and any medications used as treatment. When this information is collected by the site, the site staff will record it on the subject's medical record.

The period of observation for adverse events extends from the time the subject receives vaccination until he or she completes the safety follow up period (Day 29) or terminates the study earlier.

Any medical event that occurs after the informed consent form is signed, but prior to receiving study vaccine and is related to a study procedure, will be documented as an adverse event and recorded on the Adverse Events CRF. Any medical event that occurs after the informed consent form is signed, but prior to receiving study vaccine and is not related to a study procedure, will be documented as a pre-existing condition and will be recorded on the Medical History CRF.

All adverse events, regardless of severity, will be monitored by the investigator until resolution or stabilization. All subjects experiencing adverse events - whether considered associated with the use of the study vaccine or not - must be monitored until symptoms subside and any abnormal laboratory values have returned to baseline, or until there is a satisfactory explanation for the changes observed, or until death, in which case a full pathologist's report should be supplied, if possible. All findings must be reported on an "Adverse Events" CRF and on the "Vaccine Serious Adverse Event" form, if necessary, which is part of the investigator's study file. All findings in subjects experiencing adverse events must be reported also in the subject's medical records.

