7.0 STATISTICAL PLAN

7.1 Statistical Hypothesis

All analyses will be run descriptively; no statistical (null) hypothesis is associated with the primary safety objective.

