7.2 Sample Size and Power Considerations

A total of approximately 3,300 subjects are planned for enrolment into this study. Assuming a 10% drop-out rate, this should provide approximately 3,000 evaluable subjects. This sample size meets the post-licensure requirements of the KFDA to provide continued safety monitoring in the Korean population.

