2.2 Number of Subjects

A total of approximately 3,960 subjects are planned for enrolment into this study.

Assuming a 10% drop-out rate, this should provide approximately 3,000 evaluable subjects in the cohort 2 to 55 years of age and 600 in the cohort 2 to 23 months of age. This sample size meets the post-licensure requirements of the MFDS to provide continued safety monitoring in the Korean population.

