4.1 Safety Endpoints

Safety will be assessed after administration of study vaccine in terms of the number and percentage of subjects with:

- Local and systemic solicited adverse events reported from study Day 1 (day of vaccination) through study Day 7 post-vaccination;
- Unsolicited AEs reported from study Day 1 (day of vaccination) through study Day 7 post-vaccination;
- Medically attended AEs reported from study Day 1 to study termination (Day 29/early termination);
- SAEs reported from study Day 1 to study termination (Day 29/early termination).

5. Assessment Criteria

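### A Day 29 call for serious and medically attended events should be required, not just recommended, for vaccinated subjects who stop early and still accept contact

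*Protocol*

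**What the plan says.** **Ending participation.** Protocol section 4.3 lets subjects withdraw consent at any time. It also lets the investigator withdraw a subject when "it is in the best interest of the subject or if the subject cannot comply with the protocol". It foresees withdrawals that result from an adverse event and asks for that information in the CRF. Withdrawn subjects are not replaced.

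**End of observation.** Under section 6.2.5, adverse events are observed "until he or she completes the safety follow up period (Day 29) or terminates the study earlier". SAP V6.0, section 4.1, has the same limit for the endpoint: "SAEs reported from study Day 1 to study termination (Day 29/early termination". Medically attended events have the same window.

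**After early termination.** Note g to Table 3.3-1 reads: "Any subject who terminates the study during the Post-Vaccination period is recommended to undergo Day 29 study-related procedures". By contrast, section 3.3 makes a phone contact mandatory, with at least three attempts, when the Diary Card has not been retrieved within 10 days after Day 29.

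**Analysis.** The Safety Set (protocol 7.3, SAP 3.1) holds every vaccinated subject with post-vaccination safety data. SAP 6.2 plans a proportion with a normal-approximation interval.

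**Amendments.** The full amended protocol is not in the documents. The logs show no change to section 4.3. Amendment 3 shows a revised Times and Events Table in which study termination carries note h, but the notes themselves are not reproduced. It also adds a sentence to section 3.4 on following safety to the end of the surveillance period, without saying whether withdrawn subjects are covered.

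**The concern.** From 2 years of age there is one dose, given on Day 1. Ending participation after that cannot spare the subject any study treatment; it only stops data collection. (Infants of 2 to 23 months may have later doses under surveillance, so for them this is only partly true.) A subject who finds the diary too much, or whom the investigator takes out for another reason, may be perfectly willing to answer one phone call on Day 29, yet the note leaves that call optional.

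Serious and medically attended events through Day 29 are two of the four components of the primary objective, counted whatever their cause. If subjects who stop early are more likely than others to have such an event, missing their later days pulls the reported proportions down. Because the study is descriptive ("All analyses will be run descriptively; no statistical (null) hypothesis is associated with the primary safety objective"), no error rate is affected; what suffers is the accuracy of the proportions the study exists to report.

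**Working it through.** **Step 1. What is still captured after early termination**

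| Event | Governing text | Captured? |
|---|---|---|
| Began before termination | 6.2.5: all AEs followed to resolution or stabilisation; 3.3: SAEs to resolution or identified cause | Yes |
| Starts later, considered vaccine-caused | 6.2.5, Post-Study Events: must be reported to the sponsor | Reportable |
| Starts later, not judged vaccine-caused, diary not retrieved | 3.3: phone contact, at least three attempts, no stated exception for withdrawn subjects; note g: recommended only | Unclear |
| Starts later, not judged vaccine-caused, diary already handed in | Note g only | Not required |

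The gap is the last row, and possibly the third.

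**Step 2. What the analysis does with the missing days**

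Protocol 7.6 treats anyone vaccinated with some safety data as evaluable. No minimum follow-up, person-time or missing-data rule is stated. The Safety per protocol set removes subjects whose safety information cannot be established because of loss to follow-up, but does not say whether partial follow-up qualifies. A subject last seen on Day 10 therefore counts in the Safety Set denominator as fully as one seen on Day 29.

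**Step 3. Form of the bias**

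Let p be the Day 1–29 risk in completers, d the share of *analysed* subjects who stopped early, RR their risk relative to completers, and f the share of early stoppers with an event whose only qualifying event falls in the gap of Step 1.

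- True proportion: p[(1 − d) + d·RR]
- Observed proportion: p[(1 − d) + d·RR·(1 − f)]
- Share of affected subjects missed: d·f·RR / (1 − d + d·RR)

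This is never negative, so the direction is downward whenever d and f exceed zero.

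**Step 4. Can the 10% drop-out stand in for d?**

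The protocol (7.2) says "A total of approximately 3,300 subjects are planned for enrolment into this study" and "Assuming a 10% drop-out rate, this should provide approximately 3,000 evaluable subjects". Check: 3,000 × 1.10 = 3,300, and 3,300 × 0.90 = 2,970, close to 3,000. SAP V6.0 (2.2) says "A total of approximately 3,960 subjects are planned for enrolment into this study", for 3,000 + 600 = 3,600 evaluable: 3,600 × 1.10 = 3,960, and 3,960 × 0.90 = 3,564. The figures reproduce as approximations.

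That 10% takes enrolled subjects to evaluable ones. Evaluable already means vaccinated with some safety data, so the planned drop-outs lie outside the analysed set. The quantity d lies inside it. The 10% is therefore the wrong input, and the documents give none of d, f or RR.

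**Step 5. How the formula behaves, on assumed inputs only**

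With f from 0.25 to 0.75 and RR from 1 to 5:

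- d = 1%: from 0.01 × 0.25 × 1 / 1.00 = 0.25% to 0.01 × 0.75 × 5 / 1.04 = 3.6%
- d = 3%: from 0.03 × 0.25 × 1 / 1.00 = 0.75% to 0.03 × 0.75 × 5 / 1.12 = 10.0%

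All three inputs are assumptions. The range shows only that the answer depends almost wholly on numbers the plan does not supply.

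**The case against.** The case against acting is reasonable. A subject who leaves because of an adverse event must be followed while that event lasts, so contact does not stop at the moment of withdrawal. If the event was itself serious or medically attended, the subject is already in that numerator, because the endpoints count subjects. The phone rule for unreturned diaries has no stated exception for withdrawn subjects and would catch the commonest form of non-compliance. A recommendation also respects the right to withdraw consent. Reporting is open: withdrawals due to adverse events are listed (protocol 7.6.3) and reasons for not completing are tabulated (SAP 6.3). Finally, note g is version 1 text, and Amendment 3's sentence in section 3.4 may have extended follow-up.

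Most of this stands, and it narrows the point. It does not close it. Following an existing event is not the same as asking about new ones. The phone rule is tied to retrieval of the diary, so it does nothing once the diary is in. Tabulating reasons shows how many stopped, not what happened to them. Respect for consent justifies a recommendation for those who refuse contact, but not for those whom the investigator takes out. As for the amendments, the logs show no change to 4.3, and SAP V6.0 still ends the window at early termination.

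**Conclusion.** A real but narrow gap, and a cheap improvement rather than a flaw that undermines the study. New serious or medically attended events, not judged vaccine-caused, that begin between early termination and Day 29 have no assured route into the data. The bias is towards under-reporting, and its size cannot be derived from the documents. The conclusion rests on the version 1 wording of the note; the current wording cannot be checked.

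A reader might infer three stronger things that the documents do not support:

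- That withdrawal ends all adverse event observation. It does not: sections 3.3 and 6.2.5 keep begun events under follow-up and make later vaccine-caused events reportable.
- That subjects withdrawn for an adverse event are followed less closely than those who silently fail to return a diary. The duty to monitor existing events, and a phone rule with no stated exception, contradict this as a general statement.
- That the loss can be sized from the 10% drop-out. Step 4 shows why it cannot.

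Nor do the documents show that follow-up stops selectively. Drop-out is not split by reason, and section 4.3 does not name an adverse event among the investigator's own grounds for withdrawal.

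**What to change.** 1. In the early-termination note of the current Times and Events Table, turn the recommendation into a requirement. Every vaccinated subject who stops early and has not withdrawn consent to contact has a Day 29 phone contact covering serious and medically attended events, under the three-attempt rule of section 3.3.
2. In section 4.3, separate withdrawal of consent from participation ended by the investigator. State that failure to keep the diary ends diary collection only.
3. Reconcile sections 3.3, 4.3 and 6.2.5, the table note and Amendment 3's section 3.4, so that it is clear whether the unreturned-diary call and the follow-up to the end of surveillance apply to withdrawn subjects.
4. Where follow-up has already closed, report its completeness by reason for termination beside the SAP 6.3 table, so that readers can judge the possible loss.

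The cost is a wording change and a few extra calls, using a procedure that sites already follow.
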